3.0 BACKGROUND AND RATIONALE

3.1 Respiratory motion in lung cancer radiation treatment

Non-small cell lung cancer (NSCLC) remains the malignancy associated with the highest number of cancer-related deaths in the US.

Patients with inoperable early-stage NSCLC are typically treated with high-dose stereotactic body radiation therapy (SBRT) resulting in excellent local control of >90%. [2-5] SBRT is now also being used for metastatic disease in the lungs, with equally good local control rates and low rates of toxicity as observed in early-stage NSCLC. [8-11] Currently, a 4D free breathing CT scan is obtained at simulation. The 4D scan is used to determine the entire volume swept out as the tumor moves through the respiratory cycle. This volume (the ITV) is further increased by the addition of 0.5 to 1 cm margins of healthy tissue to create the volume (the target) which is treated to the prescription dose. The margins of healthy lung are needed to account for positioning uncertainties during treatment. Significant respiratory tumor motion results in an increase of the ITV and therefore the volume of healthy lung within the target volume. The volume of healthy lung within the target, and the volumes of adjacent normal tissues such as chest wall increase rapidly with increasing ITV size. Since these patients are usually medically inoperable due to severe emphysema or other medical comorbidities, any reduction in radiation dose to organs at risk is desirable. The most common toxicities observed with SBRT include respiratory toxicity, esophagitis, chest wall pain, and rib fractures. The rate of toxicities from SBRT appears to be directly related to the irradiated volume, the tumor

location and the radiation dose.[5-7]

Locally-advanced NSCLC patients receive fractionated RT, ideally 60 Gy in 30 fractions when given with concurrent chemotherapy.[12-14] Frequently, the predicted toxicity from radiation dose to the lungs and spinal cord using widely agreed upon dose constraints to these organs limit our ability to treat patients to the optimal prescription dose. [15, 16] Respiratory motion can significantly increase the treated volume, especially in patients with already large tumors. The most common toxicities in this patient population are esophagitis and respiratory toxicity including radiation pneumonitis.[14, 17] The same challenges exist for patients with limited-stage small cell lung cancer treated with chemotherapy and thoracic radiation therapy.[18-20] Techniques to address intrafraction tumor motion include abdominal compression, respiratory gating, and active breathing control (ABC).[21] While these are all clinically approved techniques, they are not currently widely used in practice. Abdominal compression can be uncomfortable to the patients and does not necessarily control internal motion well.[22] In addition, it compresses the lungs and does not consistently improve sparing of normal tissues, but may actually worsen the dosimetry.[23] Respiratory gating based on external markers can be misleading due to the potential discrepancy between external marker and true internal target motion.[24, 25] ABC is an involved process using a spirometer which is frequently uncomfortable to the patient, and there are problems with changes in tidal volume, volume expansion, patients' response and adaptation to the system.[26, 27] These techniques all depend on unreliable surrogates of the target position, and frequently cannot be tolerated by patients because of patient discomfort or are too complex for patients to manage, making them far from ideal .

In principle, DISH is a promising approach to minimize respiratory motion. It has been shown to reduce respiratory motion, increase lung volume, and allow dose escalation.[1, 21, 28, 29] Currently, DISH is feasible in about 25% of patients who undergo lung radiation therapy. This is because of the difficulty many patients have in adequately performing the modified slow vital capacity maneuver currently used for DISH, which consists of a deep inhalation, deep exhalation, second deep inhalation and breath hold. When performed well, the maneuver results in a reproducible lung inflation and thereby tumor position. We currently use it in selected patients who are able to perform this maneuver well. Currently, DISH is based on external markers e.g. RPM, or radiographic surrogates such as the diaphragm, since lung tumors are typically not well enough delineated on 2D radiographs. However, DISH based on surrogates like external markers and radiographic surrogates such as the diaphragm is fraught with the same problems as respiratory gating based on external markers or the ABC device. There may be a lack of correlation between external marker and internal target motion, e.g. drifts or shifts of the internal target that may not be accurately detected by an external marker.[24, 25]

We therefore propose using implanted Calypso lung transponders for guidance and monitoring of DISH in patients with thoracic malignancies who are treated with radiation therapy. This would represent a significant improvement over current DISH techniques

by having available reliable, real-time tumor position information prior to and throughout the radiation treatment delivery. With real-time tumor position feedback, it will not be necessary to perform the difficult DIBH maneuver; instead, a simple inhalation and breath hold will be sufficient to position the tumor with high reproducibility. We expect this to substantially improve the patient eligibility rate compared to other methods for DIBH guidance, such as spirometry or external markers. As a result, we expect to more frequently be able to treat patients with locally-advanced lung cancers to the intended total dose of 60 Gy as a direct benefit to patients from using this technique. If successful this study will lead to a new clinical technique that will allow us to decrease the volume of healthy lung and adjacent tissues exposed to high doses, thus further decreasing the risk for toxicities. This makes possible a strategy for dose escalation and thus the potential for improved local control in patients where current treatments are limited by normal tissue constraints.

3.1.1 Rationale for the use of Calypso lung transponders

In prostate cancer RT, the use of electromagnetic Calypso transponders has been found to allow real-time tracking of inter- and intrafraction motion, as well as reduction in PTV margins and patient-reported acute morbidity.[31-33] Submillimeter accuracy was established to a range of 27cm distance from the detection array and at speeds of up to 3cm/s, thus making it the most accurate real-time motion monitoring device available.[34] Electromagnetic Calypso transponders revealed prostate motion of >5mm in 97% of patients, thus providing a significant benefit over conventional patient positioning. In addition, a cost-utility analysis demonstrated significant benefits in quality-adjusted life years (QALY) compared to conventional localization.[35] Outside of prostate cancer, these transponders have been shown to also be feasible for inter-and intrafraction motion detection in pancreatic cancer.[36] The implantation of the transponders as part of the staging laparoscopy was well-tolerated and minimal migration of the transponders was observed. It was shown that breathholding significantly decreased tumor motion.

Until recently, no such transponder system was available for lung tumors, due to the difficulty of developing a transponder that would stay fixed after implantation. Varian Medical has now developed a modified transponder for use in lung cancer by adding anchors to the same transponders that are in routine clinical use for prostate cancer. The anchors of the lung transponder stabilize the transponder in small airways of the lungs. A pilot study from the University of Stellenbosch, Tygerberg, South Africa, and the University Hospital Basel, Basel, Switzerland, has found the first use in humans to be safe and feasible.[22, 37] No patients developed pneumonia, pneumothorax or adverse pulmonary symptoms. Significant intrafraction variability of tumor motion was detected, even with the use of external compression devices. Currently, these anchored transponders are being tested for safety and feasibility in the lungs in an ongoing larger clinical study ("Evaluating an Anchored Transponder in Lung Cancer Patients Receiving Radiation Therapy" (NCT01396551), www.clinicaltrials.gov). Preliminary findings of this study in the US showed that out of 48

evaluable patients, two patients experienced a pneumothorax (Grade 2), one patient had anesthesia-related cardiac arrest (Grade 4), two patients experienced cough (Grade 2) and one patient had dyspnea (Grade 2) after the bronchoscopy, one patient had lung infection (Grade 3), and two patients had migration of one fiducial marker each that did not impact the ability to track the tumor during radiation treatments.[38, 51.] The use of Calypso transponders holds the potential for a great benefit of real-time tumor position information without the use of ionizing radiation from additional intrafraction imaging. Calypso transponders have been routinely used in our department as a motion monitoring system for prostate RT for about 5 years. The entire system including 4D console, electromagnetic array, tracking station and optical system is in place on a linear accelerator that is equipped for lung RT and on-board kV imaging.

3.1.2 Rationale for the use of SuperDimension® system and radial probe Endobronchial Ultrasound

The SuperDimension® system is an electromagnetic navigation bronchoscopy (ENB) system that allows minimally invasive procedures in the periphery of the lungs with higher accuracy than conventional bronchoscopy alone[39]. It allows bronchoscopic biopsies, fine needle aspirations and fiducial marker placements with a reduced risk of pneumothorax as compared to transthoracic approaches. Given its extended range it has been shown to reach peripheral lung tumors with accuracy >80%. This system allows for virtual guidance based upon CT reconstructions and electromagnetic tracking. Therefore, real-time confirmation can be provided by radial probe endobronchial ultrasound (rEBUS; Olympus Medical) which further improves the accuracy.[40, 41] In certain cases, rEBUS alone is sufficient to localize peripheral pulmonary lesions.[42-45] However, it has been shown that the combination of these technologies provides the highest diagnostic yield for biopsies of peripheral lung lesions by improving lesion localization accuracy. Both of these localization technologies are in routine use by our interventional pulmonologists and thoracic surgeons and are fully compatible with the Calypso anchored transponder system.

Prior studies have demonstrated safety in placing other fiducial markers bronchoscopically (ENB +/- rEBUS) for lung tumors with low migration rates and low pneumothorax rates.[46-48] Comparisons of transcutaneous versus ENS-guided fiducial marker placement shows a higher risk of pneumothorax in the transcutaneous group.[48] Furthermore, early studies in Switzerland and South Africa have shown the feasibility, stability and safety of bronchoscopic Calypso transponder placement.[37] We therefore propose to use the SuperDimension ENB system and rEBUS for the placement of Calypso transponders whenever possible. Alternatively, conventional bronchoscopy may be used for Calypso transponder placement where feasible. Radial probe endobronchial ultrasound (EBUS) may be used when needed for more accurate placement of the Calypso transponders.

3.2 Preliminary Data

DIBH has been previously explored using coached breath-hold monitored by spirometry [28, 49] and radiographic imaging and using spirometry plus the Elekta "ABC device" together with radiographic imaging[21][18, 27]. An initial series of 5 patients at MSKCC who underwent CT scans under 4 different respiration conditions including DIBH showed that DIBH can reduce the volume of lung receiving more than 25 Gy by 30% compared to free-breathing radiation plans. Patients were able to comfortably hold their breath for 12 -16 seconds and perform 10-13 breath-holds in a single session.[28]

We then showed that coached DIBH with spirometer monitoring decreased estimated normal tissue complication probabilities while allowing for increased tumor doses.[1] Patients were initially maintained at quiet tidal breathing, followed by a deep inspiration, a deep expiration, a second deep inspiration, and breath-hold in deep inspiration (DIBH). Simulation, verification and radiation treatments took place during this last phase of DIBH. Seven patients received a total of 164 treatment sessions with excellent tolerability. None of the seven patients needed to discontinue treatment or resume the free-breathing backup method due to fatigue or inability to perform the DIBH maneuver. On average, the radiation dose could be increased from 69.4 Gy to 87.9 Gy without increasing the risk of toxicity by using DIBH.

In a subsequent analysis of 7 patients undergoing over 250 treatments, we found that reproducibility was excellent as judged by spirometry and verification films using the diaphragm as a surrogate. Presumed respiration-dependent tumor motion was thus significantly reduced from $0.8 +/- 0.5\text{cm}$ to $0.02 +/- 0.14\text{ cm}$ (mean and standard deviation) compared to free breathing.[49] The main advantages observed with the use of DIBH were an increase in lung volume and motion of the PTV away from critical structures, e.g. spine. Thus, DIBH is an excellent tool to decrease target motion, decrease radiation dose to normal organs at risk and thus allow dose escalation to the tumor. DIBH treatments are currently clinically used in our department in appropriate patients. However, all DIBH treatments to date have relied on external or indirect markers as surrogates, sometimes combined with fluoroscopy or radiographic imaging for position verification. Given the potential pitfalls of external surrogates, we propose to investigate and improve DIBH treatment delivery using real-time tumor position information from implanted electromagnetic Calypso anchored transponders. In addition, the use of Calypso anchored transponders would simplify the DIBH maneuver to a single, comfortable breathhold, thus making it an attractive treatment option for a wider patient population.

Early studies in Switzerland and South Africa have shown the feasibility, stability and safety of bronchoscopic Calypso anchored transponder placement.[37] They have also demonstrated successful intrafraction motion detection.[22] An ongoing prospective international trial explores the safety and feasibility of endobronchial implantation of these electromagnetic fiducials. Interim results reported at ASTRO 2012 showed that 149 transponders were successfully implanted in 48 patients.[38, 51.] Two patients developed cough (G2), 1 patient

had dyspnea (G2) after bronchoscopy, two patients had pneumothoraces (G2), one patient had an anesthesia-related cardiac arrest (G4), and one patient had a lung infection (G3) concurrent with marker migration. One other patient experienced an asymptomatic migration of one transponder in a large airway that did not prevent localization and tracking by the Calypso system. Positional stability of these transponders is therefore 99% to date.

4.0 OVERVIEW OF STUDY DESIGN/INTERVENTION

4.1 Design

The primary objective of this study is to evaluate the feasibility of Calypso transponders as an internal tumor surrogate to guide DIBH radiation treatments in real time.

The use of Calypso transponders has the potential to result in improved reproducibility of tumor positioning during DIBH treatments. We therefore plan to analyze the obtained respiratory traces from the Calypso signal as well as the imaging data from CBCTs and radiographs to explore a set of secondary objectives. These include a comparison of the reproducibility of DIBH tumor position with visual versus without visual biofeedback (for patients who agree to use the digital goggles), measurement of any residual intrafraction tumor motion, improvement in normal tissue dosimetry during DIBH based on the Calypso lung transponder signal as a surrogate, and determination of any increase in dose escalation and the potential for decreasing margins made possible by Calypso-guided DIBH. Given the successful radiation localization in the first 25 patients, we will also aim to determine the minimum clinically feasible gate margin for radiation. We will reduce the gate from +/-5mm by 1mm for every 5 patients treated. Once the minimum gate is determined, the remaining patients will be treated at +1mm from this value. We will also plan to enroll at least 10 additional conventionally fractionated patients to assess the impact of tumor shrinkage on beacon position and centroid changes. Finally, lung volume preservation will be assessed on wide field of view cone-beam CTs and compared intra- and interfraction within each patient to check for reproducibility or variability of lung volumes across multiple DIBH maneuvers.

The radiation treatment for patients on this study will be performed according to routine procedures using standard equipment, techniques and treatment planning procedures. The radiation dose prescription criteria will not be changed based on the DIBH maneuver or Calypso transponder implantation on this study. Patients will be followed as per our institutional standard at approximately 3, 6, 9 and 12 months after radiation treatments. Following completion of study participation, patients will be followed as per our institutional standard. They will be evaluated for any potentially transponder-related toxicity. Any toxicities will be carefully evaluated case by case according to the Common Terminology Criteria for Adverse Events (CTCAE) v4.0.

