procedures based on external tattoos and room lasers. A free- breathing trace of the Calypso transponders will be obtained to allow the patient to settle on the treatment table and to study real-time respiratory traces. The patient will then be asked to perform a therapist-coached modified slow vital capacity maneuver and DIBH maneuver [1] and hold their breath. Patients will have the ability to perform this maneuver with or without biofeedback from digital goggles that are placed over the patient's eyes and display the breathing trace of the Calypso transponders. The use of the digital goggles will be determined by patient preference or at the discretion of the treatment team. This will allow us to investigate whether real-time biofeedback adds to the reproducibility of patients holding their breath. A DIBH cone-beam CT will be acquired in approximately three breath-holds, once a week for standard fractionated RT patients or with each fraction for SBRT patients. After review and approval of the images, the patient will be treated while holding their breath using the DIBH maneuver. In standard fractionated RT patients the radiation treatment will be guided by the external tattoos and daily 2D kV imaging. The Calypso transponder signal will be used to monitor the level of the breath-hold during treatment. The breath-hold level based on the Calypso transponder signal will be verified daily by the 2D imaging and once a week in 3D by the DIBH cone-beam CT. In SBRT patients, the radiation treatment will be guided by the external tattoos and daily DIBH cone-beam CT. The Calypso transponder signal will be used to monitor the level of the breath-hold during treatment. The therapists will monitor the respiratory trace signal from the Calypso transponders throughout the treatment and will initiate the radiation treatment delivery when the patient holds his/her breath within the tolerance level the patient has been assigned to. This will be continued up until the initially planned 30 patients are accrued.. Should the transponder signal indicate that the target has moved outside of the preset tolerance, the therapists will hold further radiation treatment delivery until the patient's breathhold has returned to the desired target range or until the patient's setup has been corrected. In the additional 25 patients planned, the margins will be reduced in a step-wise fashion. The gate will be decreased 1mm per each set of 5 patients until the duty cycle (beam-on time) and number of DIBH attempts are doubled. The gate at which this occurs will be considered the minimum clinically feasible gate

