Reproducibility of using internal tumor surrogates (Calypso beacons) during repeated deep inspiration breath hold maneuvers with and without visual biofeedback will be evaluated by posthoc analysis of the Calypso signal traces. The ability to maintain the breathhold to within the tolerance level to which they have been assigned will be assessed. Number of beam holds and treatment interruptions will be recorded as an objective measure of the patient's ability to maintain their breathhold. Whether or not visual biofeedback will aid in the ability to hold their breath reliably and within the target region will be assessed using the number of treatment interruptions. We will also assess differences in duty cycle and number of DIBH attempts with and without visual biofeedback. Differences in the ability of maintaining the DIBH maneuver within the gate with and without visual biofeedback will be measured as duty cycle, a quantifiable measure of how long it takes to deliver a radiation treatment. It is related to how well patients can hold their breath and the tumor in the target position. Each patient will have the goggles 50% of the treatments and without goggles the other 50% of the time. Wilcoxon rank sum tests will be done to compare the duty cycle.

The residual intrafraction motion and drift during DIBH will be determined based on the Calypso signal traces which may provide critical insight into the ability to immobilize the tumor by DIBH. Beacon position stability will be determined on acquired cone-beam CTs by measuring the distance of the beacons to the center of the gross target volume {GTV} as well as the distance of the beacons to each other. Improvement of normal tissue dosimetry based on Calypso-guided DIBH will be determined from the treatment plans developed on the free-breathing and DIBH simulation CT scans. Specific dosimetric parameters will include the chest wall V30, total lung V20, mean lung dose, lung toxicity model metrics (Lyman model NTCP and parallel model fraction damaged (fdam)), mean and maximum esophageal dose, and maximum spinal cord dose.

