To determine the minimum clinically feasible gate margins we will decrease the gate in a step-wise progression as far as a minimum of 2 mm. The gate will be reduced from +/- 5mm by 1mm for every 5 patients treated. Halving of the duty cycle will be considered the minimum gate that is clinically feasible. Once the minimum gate is determined, the remaining patients will be treated at +1mm from this value.

In the additional 10 conventionally fractionated patients, tumor shrinkage will be summarized as relative shrinkage in a percentage. Beacon position and centroid are 3D coordinates that will be determined as a distance from a landmark such as a bone or the carina.

Lung volume preservation will be assessed on wide field of view cone-beam CTs and compared intra- and interfraction within each patient to check for reproducibility or variability of lung volumes across multiple DIBH maneuvers.

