For the 1st secondary objective, we will compare the visual vs no visual biofeedback treatments (for patients who agree to use the digital goggles) by the number of treatment interruptions. We expect that there will be fewer treatment interruptions when using biofeedback. To this end Wilcoxon signed-rank tests will be conducted based on the patients who can successfully be treated.

For the 2nd secondary objective, we will assess differences in the ability of maintaining the DIBH maneuver within the fate with and without visual biofeedback. Such differences will be measured as duty cycle, and will be compared using Wilcoxon signed-rank tests based on the patients who can successfully be treated.

For the 3rd secondary objective, the residual intrafraction tumor motion (surrogated by Calypso) will be measured in all 3 dimensions and the euclidean distance will be calculated, which will then be correlated with the normal tissue dosimetry (see end of Section 12.0). Patients will receive multiple fractions and thus multiple measurements of such distance will be obtained from the same patients.

These repeated measures will be averaged for each patient and the correlation will be examined by simple linear regression. If such continuous data are skewed, we may either use an appropriate monotone transformation, or examine the nonparametric correlation coefficient (such as Spearman rank correlation coefficient) between the tumor motion and the normal tissue dosimetry instead.

For the 4th secondary objective, the potential increase in dose escalation and decrease in margins made possible by Calypso- guided DIBH, as contrasted to those obtained from the 40 CT scan, will be formulated as pair data from each patient and tested by using Wilcoxon signed-rank tests. Dosimetric parameters listed at the end of Section 12.0 will be used again for such analysis.

The 5th secondary objective does not require statistical analysis. See Section 12.0 for details.

For the 6th secondary objective, tumor shrinkage, beacon position and centroid changes in conventionally fractionated patients (totally 10), all measured as continuous variables, will be summarized descriptively.

For the 7th secondary objective, intra- and inter-fraction variation in lung volume preservation of multiple DIBH maneuvers will be recorded within each patient and summarized descriptively.

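### The minimum-gate objective observes each 1 mm step in a different set of five patients, with no stated reference and no planned analysis, so patient differences, including any shift in SBRT/conventional mix, are confounded with the gate

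*Combined protocol and SAP*

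**What the plan says.** Section 1.0 says that in the additional 25 patients the gate will be "decreased 1mm per each set of 5 patients until the duty cycle (beam-on time) and number of DIBH attempts are doubled", and that the gate at which this happens is the minimum clinically feasible one. Section 4.1 gives the starting point: "We will reduce the gate from +/-5mm by 1mm for every 5 patients treated". Section 12.0 sets the floor, "decrease the gate in a step-wise progression as far as a minimum of 2 mm", and words the criterion differently: "Halving of the duty cycle will be considered the minimum gate that is clinically feasible". Sections 4.1 and 12.0 both treat the remaining patients at 1 mm above the gate so found.

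Section 12.0 describes duty cycle as "a quantifiable measure of how long it takes to deliver a radiation treatment". Section 6.1 leaves SBRT or standard fractionation to the treating physician, and Section 15.2 states that there is no randomization. Section 4.1 adds "We will also plan to enroll at least 10 additional conventionally fractionated patients", for the tumor-shrinkage objective. On the analysis of the minimum gate, Section 14.0 says: "The 5th secondary objective does not require statistical analysis", and refers to Section 12.0.

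**The concern.** Each gate is seen only in its own five patients. A change in the set-level figure from one gate to another is therefore the gate effect multiplied by whatever difference there is between the patients. Nothing in the plan separates the two: no reference set, no summary statistic, no allocation or adjustment by fractionation, no within-patient comparison. The only stratification in Section 14.0 separates the first and second sets of 25 for the primary objective.

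Fractionation is one plausible source of difference. Beam-on time and number of breath-holds per fraction may well rise with dose per fraction. Conventional treatment is ideally 60 Gy in 30 fractions, or 2 Gy each (Section 3.1), and SBRT is given in 10 fractions or fewer (Section 9.1).

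The minimum gate is a named secondary objective, and it also sets the gate for the patients still to be treated. A chance difference between sets could place it too wide or too narrow.

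**Working it through.** The documents give no sample size or operating characteristic for this rule, so there is no stated figure to reproduce.

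**Inputs from the documents.** Sets of 5; start at +/-5 mm; floor of 2 mm, hence at most three reductions (4, 3 and 2 mm); 25 patients in the extension; at least 10 conventional patients. The ten are read as part of the 25 because Section 14.0 gives a total of 55 = 30 + 25. This is an inference.

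**Assumptions.** R is the ratio of the per-fraction measure in SBRT to that in conventional patients, at an unchanged gate; range 1 to 4. The between-patient CV is 0.3 to 0.8, lognormal. Exactly 10 of the 25 are conventional, falling at random across sets.

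**1. How far the mix moves by chance.** The number of conventional patients in a set is hypergeometric, C(10,k) × C(15,5−k) / C(25,5). Two given sets differ by 2 or more conventional patients with probability 34%, and by 3 or more with probability 11%. At least one of the three reduced-gate sets differs from the first set by 3 or more with probability 25%.

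**2. What mix alone does.** With k conventional patients the expected set mean is (k + R(5 − k))/5.
- R = 3, from 4 to 1 conventional: (1 + 12)/(4 + 3) = 13/7 = 1.86, short of doubling.
- R = 2: only a full switch from 5 to 0 conventional reaches 10/5 = 2.0.
- R = 1.5: doubling cannot be reached.

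**3. Masking needs less.** Take a true 2.0-fold gate effect and one more conventional patient (from 2 to 3).
- R = 2: 2.0 × (3 + 4)/(2 + 6) = 2.0 × 7/8 = 1.75.
- R = 3: 2.0 × (3 + 6)/(2 + 9) = 2.0 × 9/11 = 1.64.

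**4. Simulated rule.** One measure is used. The reference is the first set, at +/-5 mm. False doubling means a set mean at least twice the reference at 4, 3 or 2 mm with no gate effect. A miss means that a true 2.5-fold effect at the last gate shows as less than 2.

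| CV | R | False doubling | Miss |
|---|---|---|---|
| 0.3 | 1 | 0.0% | 11.6% |
| 0.3 | 2 | 1.8% | 21.4% |
| 0.3 | 3 | 6.6% | 26.6% |
| 0.5 | 1 | 3.5% | 23.5% |
| 0.5 | 2 | 8.3% | 27.8% |
| 0.5 | 3 | 13.8% | 30.5% |
| 0.8 | 1 | 17.8% | 32.0% |
| 0.8 | 3 | 25.9% | 35.0% |

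The R = 1 rows are pure between-patient noise. With the previous set as reference, false doubling at CV 0.5 is 3.9%, 10.1% and 18.5% for R = 1, 2 and 3.

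**5. Holding the mix fixed** at 2 conventional and 3 SBRT in every set, at R = 3, lowers false doubling from 6.6% to 0.1% (CV 0.3), from 13.8% to 5.3% (CV 0.5), but only from 25.9% to 20.4% (CV 0.8). Noise between patients in sets of five is what remains.

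**6. Would deciding within fractionation type work?** The chance that a set has 0 or 1 conventional patients is (3,003 + 13,650)/53,130 = 31.3%; that it has 0 or 1 SBRT patients, (3,150 + 252)/53,130 = 6.4%. About 38% of sets would have at most one patient of one type.

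**The case against.** Four points on the other side have force.

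- **The governing criterion may be insensitive to mix.** Section 14.0 refers to Section 12.0, which uses only halving of the duty cycle and leaves attempts out. If duty cycle is a beam-on fraction, as halving suggests, dose per fraction largely cancels and R is near 1. The time-to-deliver description in the same section points the other way. This stands: the mix effect on that measure is conditional on a definition that the plan leaves open. The R = 1 rows are then the rough guide, and they are not zero at CV 0.5 or above.
- **R is not in the documents.** They give no SBRT dose per fraction and no beam time or breath-hold count by fractionation. A reader might infer that SBRT fractions need more breath-holds at any gate. That is plausible, but it is an assumption.
- **The reference might be larger.** A reader might infer that each set is compared with the one before; the plan does not say so. If the reference were 25 earlier patients, false doubling at R = 3 would fall to about 0.5% (CV 0.3) and 3.7% (CV 0.5). Misses of a 2.5-fold effect would still be about 21% and 28%, because the set at the reduced gate still has five patients.
- **Section 1.0 requires both measures to double.** This makes false doubling rarer than with one measure, but misses more frequent. The amount depends on how closely the two move together.

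It is also fair that this is one of seven secondary objectives in a nonrandomized feasibility study, and that no test is claimed for it.

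**Conclusion.** The point holds as a conditional one. The plan confounds the gate with the patients: each step rests on five different people, the reference is not stated and no analysis is planned. Case mix is one part of that. Its size runs from nothing at R = 1 to about 7% false doubling at R = 3 with CV 0.3, or 14% with CV 0.5, under random mix and the first set as reference. Masking a real effect takes a smaller shift than creating a false one.

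A reader might go further and infer that a change in mix alone is likely to reach the doubling criterion. The documents do not support that. It needs R of at least 2 and a large shift, and even at R = 3 a move from one to four SBRT patients gives 1.86. At a CV of 0.8, between-patient noise outweighs the mix. All percentages rest on the assumed R, CV and lognormal form, and on 10 conventional patients among the 25.

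**What to change.** In Sections 12.0 and 14.0, replace the statement that the objective needs no statistical analysis with a within-patient analysis of the recorded Calypso traces. For every patient, calculate the share of breath-hold time within +/-5, 4, 3 and 2 mm, and its ratio to that patient's own +/-5 mm value. Summarise these ratios over all patients and report them beside the observed set-level counts. Each patient is then their own control, which removes case mix and differences in level between patients from the comparison.

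Show set-level duty cycle and attempts by fractionation type descriptively only; strata within sets of five are too small to decide on.

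Define duty cycle, reconcile the doubling of duty cycle and attempts in Section 1.0 with the halving of duty cycle in Section 12.0, and name the reference for the change. Which wording governs is for the sponsor to settle.

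The cost is protocol wording and post-processing: the Section 10.0 schedule already lists Calypso signal recording at treatment, and Section 12.0 already plans post hoc trace analysis for reproducibility. The downside is that re-gated traces do not show how patients adapt to a tighter gate, and they give time in the gate rather than attempts. They support the observed counts and do not replace them.
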